## 9.4.3 Sensitivity Efficacy Analyses of Primary Outcome

Outlined below are various sensitivity analyses that will be conducted on the primary outcome to evaluate the robustness of the primary findings. The details of each of the planned sensitivity analyses are described below.

### Nonparametric Survival Analysis for Interval-Censored Data

This analysis will employ nonparametric maximum likelihood estimation (NPMLE) to estimate survival functions for interval censored data (censoring intervals defined as described above) stratified by randomized surgical intervention in a similar manner as the Kaplan-Meier estimator for right censored data, but also employs a combination of the EM and iterative convex minorant (ICM) algorithms to estimate the survival function in non-overlapping intervals (Wellner and Zhan, 1997) and multiple imputation is used to account for the uncertainty of ranking overlapping intervals across participants caused by missed visits. Standard errors of the survival curves and the covariance matrix for the generalized rank statistic will be generated with the multiple imputation method developed by Sun (2001). Pairwise comparisons of the surgical arms corresponding to the 3 a priori specified hypotheses testing for superiority as described above will be performed based on the generalized logrank test statistic and the corresponding variance-covariance matrix (Huang, Lee, and Yu, 2008). The log-log transformation will be used to calculate confidence intervals. The nonparametric survival analysis methods detailed above will be carried out using the ICLIFETEST procedure in SAS. The advantage of this approach is that it makes no assumptions about the distribution of the interval centered data and permits estimated survival curves to be non-monotonic (no proportional hazards assumption), although it is unable to adjust for study design and potential confounders. This analysis will primarily be used to confirm the results of the primary model-based efficacy analysis.

In addition, this analysis will serve as a way to check the assumed PWE model assumptions, particularly the proportional hazard assumption and specification of the constant underlying hazard across periods. The Kaplan Meier survival curves will be graphically evaluated to evaluate the choice of periods specified in the PWE model, should the PWE model not converge. The Epanechnikov kernel-smoothed hazard rates from the non-parametric interval-censored Kaplan-Meier analysis will be generated and graphically assessed for violation of the proportional hazard assumption.

The general structure of the SAS code that will be used is summarized below.

PROC ICLIFETEST PLOTS=ALL METHOD=EMICM CONFTYPE=LOGLOG IMPUTE(SEED=rand\_seed.) ALPHA=α STRATA treatment; TIME (LowerboundTIME, UpperboundTIME);

### **Descriptive Cross-Sectional Analysis**

This descriptive cross-sectional analysis will serve as additional support of the primary efficacy analysis methods. Each surgical failure will be categorized into the following 4 types: "retreatment failure", "anatomic failure", "symptomatic failure", and "anatomic and symptomatic failure" where retreatment failure corresponds to retreatment for prolapse, symptomatic failure corresponds to bothersome vaginal bulge symptoms, and anatomic failure corresponds to prolapse beyond the hymen all as described above. Retreatment failure type is prioritized above the anatomic and/or symptomatic failure types. The category "anatomic and symptomatic failure" is defined when bothersome bulge and prolapse beyond the hymen were first reported at the same study visit.

This analysis will compare the proportions of surgical failures and obtain point estimates and 95% confidence intervals for pairwise risk differences between each of the mesh repairs versus the native tissue repair as well as between the two mesh repairs as well as the 2 df overall test at each year 1, 2, and 3 based on Mantel-Haenszel estimates for the common risk difference stratified by pooled site and age category (<65 and  $\geq$ 65) (event rates permitting) with Wald-type confidence intervals with the estimate of the variance of the risk difference based on Sato (Sato 1984). Descriptive proportions of surgical failure types at each year will be provided. This analysis will evaluate surgical failure by visit based on surgical failure under the permanent failure state assumption and transient failure state assumption by initial failure type and at-visit failure type respectively.

Under the permanent failure state assumption, the number of the participants at each visit includes all participants who were still participating in the study or had a failure outcome prior to withdrawal. The denominator for the cumulative failure at each visit includes all participants who were still participating in the study and attended the visit or had any failure outcome prior to their withdrawal/missed visit. Under the permanent failure state assumption, the failure type corresponding to the first failure time will be provided, where the 4 failure types are mutually exclusive, with retreatment failure prioritized above the anatomic and/or symptomatic failure types.

Under the transient failure state assumption, the number of participants at each visit includes all participants who were still participating in the study. The denominator for the transient failures at each visit includes all participants who were still participating in the study and attended the visit or who missed the visit but had a retreatment failure prior to their missed visit. The failure type corresponding to the failure at each time point will be provided, where the 4 failure types are mutually exclusive, with retreatment failure prioritized above the anatomic and/or symptomatic failure types and assumed to be a permanent stated at all subsequent visits irrespective of the participant's attendance at the visit as long as the person was still participating in the study. Anatomic and symptomatic failure components are considered to be transient conditions, and with outcomes at each time point based specifically in the measurements obtained at that time point.

A figure will be created to depict the timeline of relapse for each participant, with participants each indicated by a line corresponding to their duration in the study. The line will show the time of censoring for non-relapsed participants, the time of failure for participants that remain a failure, and the multiple times that a participant was a failure for participants with transient failure symptoms. Due to missed visits caused by COVID, it will also indicate visits that were missed.

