Note that due to COVID, there are more missed visits than would have been expected pre-pandemic, as well as remotely-attended visits with missing POP-Q exams. The calculation of the primary outcome is unchanged.

Secondary Efficacy Outcomes				
Indicator of surgical failure at post- operative visit under the permanent failure state assumption	CRF-13, CRF-12, CRF- 14/37	Binary	1-, 2-, 3- , 4-, 5-years	At each timepoint , surgical failure under the permanent failure state assumption is defined if any one of the three criteria (retreatment, anatomic, or symptomatic) is met at the timepoint's corresponding attended post-operative visit or at any prior attended post-operative visits (i.e. 6- month post-operative visits 6 months up to 60 months):
				Participants not meeting the criteria for surgical failure at the timepoint's corresponding post-operative visit (if attended) and at all prior attended post-operative visits will be considered not a surgical failure, regardless of missingness of the 3 components of the surgical outcome at any of the attended post-operative visits through the timepoint. Participants who discontinued prior to the 6- month post-operative visit will be missing the permanent failure state surgical outcome at all timepoints.
				By this definition, a subject can be defined as a surgical failure at timepoints corresponding to missed post- operative visits or post-operative visits occurring after subject's discontinuation from the study IF the subject had a surgical failure prior to the missed visit or discontinuation.
Initial failure type	CRF-13, CRF-12, CRF- 14/37	Nominal Categorical (4 levels)	1-, 2-, 3- , 4-, 5-years	At each timepoint, subjects who experience a surgical failure under the permanent failure state assumption, failure type will be defined for the initially occurring surgical failure.
				Each initial surgical failure will be categorized into the following 4 types: "retreatment failure", "anatomic

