#### Pelvic Floor Disorder

				failure", "symptomatic failure", and "anatomic and symptomatic failure" where retreatment failure corresponds to retreatment for prolapse, symptomatic failure corresponds to bothersome vaginal bulge symptoms, and anatomic failure corresponds to prolapse beyond the hymen as described in the surgical failure under the permanent failure state assumption definition above. Retreatment failure type is prioritized above the anatomic and/or symptomatic failure types.
Indicator of surgical failure at post- operative visit under the transient failure state assumption	CRF-13, CRF-12, CRF- 14/37	Binary	1-, 2-, 3- , 4-, 5-years	At each timepoint, surgical failure under the transient failure state assumption is defined if any one of the three criteria (retreatment failure at that visit or any prior visit, anatomic failure at that visit, or symptomatic failure at that visit) is met at that visit.
				Participants not meeting the criteria for surgical failure at the timepoint will be considered not a surgical failure, regardless of missingness of the 3 components of the surgical outcome at the timepoint's corresponding attended post-operative visit.
				Participants who have discontinued from the study by timepoint's corresponding post-operative visit will be missing the transient failure state surgical outcome at the timepoint.
				Participants who missed the post-operative visit corresponding to the timepoint without a retreatment failure at any prior attended post-operative visit will also be missing the transient failure state surgical outcome at the timepoint.

				By this definition, a subject can be defined as a surgical failure at timepoints where the corresponding post- operative visit is missed IF the subject is still participating in the study and had a surgical failure due to retreatment failure at any prior attended post-operative visit (i.e. post- operative visits 6 months up to 60 months).
At-visit failure type	CRF-13, CRF-12, CRF- 14/37	Nominal Categorical (4 levels)	1-, 2-, 3- , 4-, 5-years	At each timepoint, subjects who experience a surgical failure under the transient failure state assumption, failure type will be defined for the surgical failure occurring at the timepoint.

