# 9.4.2 Primary Efficacy Analysis: Model-Based Survival Analysis

This model-based approach will serve as the primary analytic method for testing the comparative efficacy of the three strategies for uterovaginal prolapse as it can control for study design and potentially confounding variables. To appropriately account for the interval censored and right censored nature of the primary outcome data, and potential violation of the proportional hazards assumption across the entire follow-up time, while controlling for study design and potentially confounding variables in assessing intervention effects, a piecewise exponential (PWE) survival model will be employed. The PWE survival model is a model in which the time scale is divided into *K* periods and the underlying hazard function, h(t), is assumed to be constant within each period such that  $h(t) = \lambda_k \exp(\beta \mathbf{X})$ , where  $\lambda_k$  is the hazard function for period *k*, and **X** is a matrix of explanatory

variables with vector  $\beta$  coefficients (Breslow 1974). This piecewise approach effectively eliminates the need to specify the distribution of the hazard function and satisfies the proportional hazards assumption if the underlying hazard is constant within each period.

Among subjects who experience a surgical failure, the time to surgical failure (primary outcome) will be interval censored (i.e. lower bound, upper bound where both bounds are non-missing and lower bound < upper bound). Subjects who do not experience a surgical failure will be right censored (i.e. non-missing lower bound and missing upper bound) at their last attended visit. Specifically, the censoring interval for implementation in interval censored analysis will be defined as follows:

- lower bound = number of months (i.e. months as intended the by visit schedule) from the surgical intervention to the *last attended visit where the subject was considered to be not a surgical failure* across all post-operative visits starting at the 6 month visit. As such, subjects who were surgical failures at the 6-month post-operative visit will have a lower bound of 1.5 months corresponding to the 6-week post-operative visit. Based on this definition, the lower bound for the primary endpoint of 3 to a maximum of 5 years can take any of the following values 1.5, 6, 12, 18, 24, 30, 36, 42, 48, 54, or 60 months.

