repair against the hypothesized null ratio of 1.0 each evaluated at a two-sided significance level of  $\alpha = 0.01$ , and corresponding 2-sided 99% confidence interval. Note that pairwise comparisons will be completed within the model that contains all 3 treatment groups.

In addition, model estimates and 95% confidence intervals for the failure probability in each surgical group will be obtained at years 1, 2, 3, 4, and 5. Model-adjusted hazard rates (estimate and 95% confidence intervals) for each period will be obtained. The hazard rates will be reported as incidence density per person-year for each of the periods. For all estimates and contrasts, pooled sites and age category categories (<65 and  $\geq$ 65) will be given equal weight.

Descriptive statistics for the analysis will also include the number of participants by treatment group censored within each time interval, the median (IQR) follow-up time by treatment group, and the model hazard rate (incidence density per person year) by treatment group within each time interval.

The general structure of the SAS code that will be used for the piecewise model is summarized below.

PROC ICPHREG PLOTS(CL TIMERANGE=(0,60))=(survival) ALPHA=&alpha. NLOPTIONS(MAXIT=500); CLASS treatment; MODEL (LowerboundTIME, UpperboundTIME)= treatment Age\_group poolsite1 poolsite2 poolsite3 poolsite4 poolsite5 poolsite6 / BASE=piecewiseexponential(INTERVALS=(12,24,36,48))/ HAZSCALE=HAZARD; HAZARDRATIO "HR" treatment / DIFF=REFERENCE; TEST treatment / HTYPE=3; BASELINE OUT=work.pwe\_surv\_haz\_estimates COVARIATES=work.pwe\_covs TIMELIST=0 to 60 by 6 SURVIVAL=\_ALL\_ HAZARD= ALL / ROWID=treatment CLTYPE=LOGLOG;

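### SAP 9.3 and 9.4.3 handle never-failed women who withdraw or miss a visit differently, so the permanent-state failure proportion by year reads low under one rule and high under the other

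*SAP*

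**What the plan says.** SAP 9.3 defines the indicator of surgical failure under the permanent failure state assumption at years 1 to 5. A woman who meets no failure criterion at the timepoint's "post-operative visit (if attended) and at all prior attended post-operative visits will be considered not a surgical failure". The only missing state it names is for women who discontinued before the 6-month "post-operative visit will be missing the permanent failure state surgical outcome at all timepoints".

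SAP 9.4.3, Descriptive Cross-Sectional Analysis, uses the same outcome. Its denominator for cumulative failure is "participants who were still participating in the study and attended the visit or had any failure outcome prior to their withdrawal/missed visit". From this come failure proportions, pairwise Mantel-Haenszel risk differences with 95% intervals, stratified by pooled site and age category, and a "2 df overall test at each year 1, 2, and 3". The section presents this as support for the primary analysis.

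The transient-state outcome has no such conflict for women who withdraw. In 9.3 a woman who has discontinued by the visit "will be missing the transient failure state surgical outcome at the timepoint", and 9.4.3 leaves her out as well.

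The survival analyses work differently. In 9.4.2, "Subjects who do not experience a surgical failure will be right censored" at the last attended visit, and the model gives the "failure probability in each surgical group will be obtained at years 1, 2, 3, 4, and 5". In 9.4.3, a nonparametric (NPMLE) analysis by arm uses the same censoring intervals and "makes no assumptions about the distribution of the interval centered data".

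**The concern.** Take a woman with no failure who withdraws at month 14. At year 3 she is a non-failure under 9.3 and absent from the denominator under 9.4.3. Two programmers, each following one section, would produce different tables, and the SAP does not say which section governs.

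Neither rule estimates the cumulative probability of failure when there is loss to follow-up. Rule 9.3 carries non-failure forward over unobserved time, so it reads low. Rule 9.4.3 keeps all past failures but removes the failure-free women who left or missed the visit, so it reads high. The crude yearly rates would then appear alongside yearly failure probabilities from a model that censors at the last attended visit, and a reader could take a gap created by the denominators for a substantive one.

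**Working it through.** **Inputs.** SAP 6 assumes 2-year success of 80% (each mesh arm) and 60% (native tissue), exponential failure, loss of at most 5% per year, and 121 women per arm. Visits are 6-monthly.

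**The plan's own figures.** Hazards: -ln(0.80)/2 = 0.1116 and -ln(0.60)/2 = 0.2554 per year, as stated. With uniform 2-year accrual, 3 years of minimum follow-up and 5% yearly loss, about 79 events are expected in the two mesh arms. Then z = sqrt(79/4) × ln(1.93) - 1.881 = 1.04, which is 85% power, as stated.

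**Formulas at year 3, no missed visits.** Per 6-month period, let q be the chance of loss and p the chance of failure. A failure counts only if the woman is still followed at the next visit.
- q = 1 - sqrt(0.95) = 0.0253
- p = 1 - exp(-h/2)
- s = (1-q)(1-p), the chance of passing one period failure-free and in the study
- A = s^6, failure-free and in the study at year 3
- F = (1-q) × p × (1-A)/(1-s), failures recorded by year 3
- Rule 9.3: F/(1-q), since only loss before 6 months is missing
- Rule 9.4.3: F/(F+A)
- Assumed true value: 1 - exp(-3h)

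**Mesh arm.** p = 0.0543, s = 0.9218, A = 0.6134, F = 0.2614.
- 9.3: 0.2614/0.9747 = 26.8%, denominator 121 × 0.9747 = 118
- 9.4.3: 0.2614/0.8749 = 29.9%, denominator 121 × 0.8749 = 106
- Assumed true: 28.5%

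**Native tissue.** p = 0.1199, s = 0.8578, A = 0.3985, F = 0.4944.
- 9.3: 0.4944/0.9747 = 50.7%, denominator 118
- 9.4.3: 0.4944/0.8929 = 55.4%, denominator 108
- Assumed true: 53.5%

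**Other assumed conditions, year 3 (rule 9.3 / rule 9.4.3).** The missed-visit rows were simulated, with each visit missed independently and failure detected at the next attended visit. The SAP gives no missed-visit rate, so these rates are assumptions.

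| Yearly loss | Visits missed | Mesh | Native tissue |
|---|---|---|---|
| 1% | none | 28.1% / 28.7% | 53.0% / 53.9% |
| 2.5% | none | 27.6% / 29.1% | 52.1% / 54.4% |
| 5% | none | 26.8% / 29.9% | 50.7% / 55.4% |
| 5% | 10% | 26.4% / 31.8% | 50.0% / 57.6% |
| 5% | 20% | 25.8% / 33.9% | 49.0% / 59.9% |

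**Risk difference, native tissue minus mesh, at 5% loss.** The assumed true value is 53.5 - 28.5, or 25.1 points before rounding. The two rules give 23.9 / 25.5 with no missed visits, 23.6 / 25.8 at 10% missed and 23.2 / 26.1 at 20%. The error is 0.4 to 1.9 points. The 95% half-width, 1.96 × sqrt(0.285 × 0.715/n1 + 0.535 × 0.465/n2), is 12.1 points with 118 per arm and 12.7 with 106 and 108.

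**Years 1 and 2.** At 5% loss with no missed visits, both rules are within about 1.3 points of the assumed true value in every arm.

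**The case against.** The best defence is that 9.3 derives a participant-level variable and never mentions a denominator, while 9.4.3 contains the only sentence that sets one, in the section that makes the comparison. On that reading an analyst has one executable rule. This is reasonable and would settle which table is produced. It does not remove the upward bias of that rule, and 9.3 does set its own missing-data rule for the outcome without pointing to 9.4.3.

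The objections on weight largely stand. The table is descriptive, and SAP 7.7 says secondary p-values and intervals are not to be judged for significance. A 5% yearly loss is a design ceiling, and the protocol's extension addendum describes follow-up so far as excellent. Remote visits during the pandemic count as attended under 9.3, so the missed-visit rate may be low, although SAP 7.3 says more visits were missed than would ordinarily be expected. The displays in SAP 14 also include completeness of the primary outcome by arm.

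Three stronger readings are tempting and are not supported:

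- A reader might infer that the survival estimates should replace the crude table. They cannot: the table exists to give the four failure types and the stratified risk differences, and the SAP itself notes that the nonparametric method does not adjust for design factors.
- A reader might infer that the survival estimates have been shown to withstand informative loss. The simulations run for this point varied loss only after a detected failure, when the woman's outcome is already fixed. Loss driven by a failure not yet detected was not tested.
- A reader might infer that any difference from the model's yearly probabilities signals an error. The model is adjusted and weights sites and age groups equally, so some difference is expected even with complete data.

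**Conclusion.** The point holds, with limited reach. The two sections conflict for never-failed women who withdraw after 6 months or miss a visit, and either rule gives a biased cumulative proportion once there is loss. At the design-maximum loss with no missed visits, the two rules differ at year 3 by about 3 points in a mesh arm and nearly 5 points for native tissue. The differences shrink to under 1 point in either arm at 1% loss and grow if visits are missed.

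These sizes rest on exponential failure at the plan's hazards, loss unrelated to failure, and equal loss and missed-visit rates across arms. Under those conditions the mesh versus native tissue risk difference is off by at most about 2 points, small against its interval, and TVM versus SC is unbiased if the hazards are also equal, as planned. The primary piecewise exponential analysis does not use either denominator and is unaffected. No formal conclusion of the trial turns on this, but the published yearly failure rates could be a few points off in either direction.

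**What to change.** 1. State one rule for never-failed women who withdraw or miss the visit, in the same words in SAP 9.3 and 9.4.3, or have 9.3 refer explicitly to 9.4.3.
2. Report cumulative failure by year from the nonparametric curves by arm (9.4.3) or the piecewise exponential failure probabilities (9.4.2). Both are already planned and censor at the last attended visit.
3. Keep the crude table for failure types and stratified risk differences. Show its denominators by arm and year, and label it as not estimating cumulative incidence.
4. Do not switch the crude table to women who attended the visit only. That would discard documented failures and would be biased if women who fail leave follow-up sooner.
5. Record the change as post hoc. SAP 12 (version 2) already reports event counts by arm, so the revision cannot be presented as made under masking.

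The cost is a few sentences in the SAP and minor programming. No new data or new model is needed.
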